#### **Sample**

We conducted a careful analysis of sample size calculations for primary analysis of the primary outcome: BMI in adolescents at 6 months post intervention. As discussed further below, we will use a mixed model ANCOVA in our primary analysis. Power calculations for this approach are given by Murray. Power in a G-RCT is influenced by five factors: number of groups (schools), number of individuals in each group (adolescents in each school), similarity of outcomes within clusters (school-level intra-class correlation [ICC] for BMI), similarity of outcomes within individuals (correlation of BMI measurements on the same student over time), and percentage of the variance that can be explained by the regression model. Using data from the **Ohio Family Health Survey**, we estimate that the school-level ICC for BMI among 9th graders in Appalachian Ohio counties is 0.023. We further estimate the over-time correlation of BMI measurements is 0.70 and that adjusting for age and gender will explain approximately 30% of the variance in BMI. With these assumptions, 10 schools per condition, and 75 students per school, we will have 82% power to detect a modest intervention effect (0.2 standard deviation difference between groups). This effect size would correspond to a difference in mean BMI between groups of 1.04 kg/m^2 if the observed variation in BMI is similar to that of all Appalachian 9th graders from the Ohio Family Health Survey (mean BMI = 23.41, SD = 5.2).

With an average of 75 mentee participants per school (50% participation rate of eligible students based on our preliminary work), we estimate that a total of 1,500 9th and 10th grade participants will be recruited over 2 years (750 per year). Further, 190 older teens will be recruited to serve as peer mentors (19 per school x 10 schools) in the MBA condition, for a study total of 1,690 high school-aged children. Recruitment of mentor and mentee participants will occur during the start of the school year (September).

At the end of the academic year, we will randomly select at least 1 PBA teacher and 5 teen mentors from each school that delivered the curriculum that year to participate in cognitive interviews. These semi-structured interviews will be conducted individually and will be audio-recorded. Audio recordings will be transcribed verbatim. Each interview will last approximately 30 minutes and will be held in a private room at each school.

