## **Participant Recruitment and Retention**

Nine school districts from 9 rural Appalachian Ohio counties have agreed to participate; an excess of 10 schools needed for Wave1. Wave 2 schools will be recruited during Year 1 of the study (with amendment to IRB protocol once letters of support are received). Peer mentors will be recruited based on interest in working with peers, supporting others, and striving to cultivate their own health-supportive behaviors. Eleventh and 12th graders attending the target high school at the study's start will be eligible to participate as mentors if they are not expected to move from the participating school before the conclusion of the study; can speak English; and are recommended by a teacher, school advisor, or counselor. Teens interested in serving as mentors will complete an application form; selection will be based on: study needs, motivation to serve, and recommendations. Teen mentors with a BMI (for age and gender) above the 85th percentile or below the 5th percentile at the start of the study will be excluded because of concerns about those not classified as having a healthy weight serving as role models for healthy lifestyle behaviors. These exclusionary criteria will be clear in recruitment materials so those excluded understand why. All teen mentors will attend the same school and reside in the same local community as study participants. Each peer mentor will be assigned up to 4 adolescents (2 per session; 2 possible sessions each week); we will recruit 19 peer mentors per school. We will attempt to match mentors and mentees by gender.

School health teachers at participating schools will provide the comparison delivery method. With approximately 25 students per classroom, we anticipate 3 classrooms to participate in each comparison school. Based on preliminary studies, an 80% retention rate is expected, resulting in 82.5% power to detect a modest intervention effect. To aid retention of subjects, monetary incentives at each data collection time-point and booster kits for use during the summer months will be provided. In addition, attendance will be taken at all sessions; the PI will contact all subjects missing a session within 48 hours.

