## **B. Detailed Study Procedures**

Anthropometric and other quantitative data will be in a designated private room at each participating high school at all data-collection time-points ( $T_1$ ,  $T_2$ , and  $T_3$ ). Questions will be read aloud to accommodate any reading difficulties and be available to answer questions. Prior to baseline data collection, a series of training sessions will be held to train data collection staff responsible for taking measurements, including physical activity using Actical accelerometers (Actical, Bio-Lynx Scientific Equipment, Montreal), BMI, body fat, and administration of the data collection instruments. The measurement team training will held at the Project Office located on the OSU campus. In order to assure standardization and quality of data collection, this training will include a review of the eligibility criteria and consent procedures; overview of the measurement protocol; demonstration of the measurement methods; and an opportunity to have each measurement team mock data collect on several subjects and gain expert feedback on their ability to follow protocol. This training will occur prior to each data collection time period ( $T_1$ ,  $T_2$ , and  $T_3$ ). The accelerometer data collection training will be done by [name]. [name] is an expert in accelerometer use and accelerometer data processing. Body fat analysis measurement training will be conducted by [name] an advanced practice registered nurse and expert in the collection of anthropometric data in community settings. The survey data collection training will be conducted by [name] and [name]. The Project Office will ensure that the measurement teams perform only those functions for which they are certified, and that re-certification activities are implemented as planned in a timely manner.

Participants will receive \$15 at each data-collection time-point. Anthropometric measures (height, weight, and body fat) will be collected from each privately. BMI will be calculated by: weight (lb)/[height (in)]  $\times 703$  (Measures). Pilot testing found anthropometric data collection will take 10-15 minutes. BMI percentiles for children will be calculated via computer using CDC guidelines. Data from peer mentors will be collected by an RA at completion of mentor training ( $T_1$ ), at the end of the academic year ( $T_2$ ), and beginning of the following academic year ( $T_3$ ). See Table 5 (next page) for the data collection plan and process.

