**Table 5: Data Procedures and Process**

Time	Process:	(Data Provided By)	Team Member
YEAR 1			
	Finalization of data collection protocols Finalization of participating schools to Waves 1 or 2 Training of PD and RAs: protocols, use of accelerometers Randomization of Wave 1 schools to either intervention or comparison	[name] & [name] [name] & [name] [name] & [name] ([name])	
WAVES 1,2			
Consent	Consent/Accent of Peer Mentors and School Participants	[name] or [name]	
End of Recruitment	1. Assignment of identification numbers to subjects, mentors, and teachers 2. Demographic Questionnaire (Peer Mentor, Subjects)	[name] Team	
Baseline (T 1 )	Subject Survey Questionnaire: Self-Report Height, weight, BEI Accelerometer – one week of data a Health Behaviors Questionnaire: (Subjects) (Subjects) (Teachers, Peer Mentors, Subjects) (Peer Mentors, Subjects)	Team	
T 1 : Follow-Up	Collection of accelerometer data (7 days)	Team	
Weekly	Debriefing sessions: observations and notations: mentors and teachers Measures of Fidelity (mentors and teachers) Data Interim Reports	[name] & [name]	
Monthly	Measures of Fidelity (mentors and Teachers)	[name] & [name]	
3 Months Post Intervention (T 2 )	Subject Survey Questionnaire: Self-Report Height, weight, BEI Accelerometer – one week of data a Health Behaviors Questionnaire (Subjects) (Subjects) (Teachers, Peer Mentors, Subjects) (Peer Mentors, Subjects)	Team	
T 2 : Follow-Up	Collection of accelerometer data (7 days) Reinforcement (Booster) Session	Team	
6 Months Post Intervention (T 3 )	Survey Questionnaire: Self-Report Accelerometer – one week of data a Health Behaviors Questionnaire (Subjects) (Teachers, Peer Mentors, Subjects) (Peer Mentors, Subjects)	RA (blinded to group)	
T 3 : Follow-Up	Collection of accelerometer data	Team	

BEI = bio-electronic impedance; aAccelerometer data collected over 3 weeks (1/3 of subjects each week to wear for 1 week)

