### C. Internal Validity

To avoid study bias, schools will be randomized for study condition (PBA or MBA). The primary analysis will follow intention-to-treat principles. Randomization carries the expectation that the study conditions will be equivalent at pretest with respect to known and unknown prognostic factors. As a result, removing randomized groups or members from the analysis runs the risk of tampering with this balance and introducing bias. Further, loss of one or more groups could create an unbalanced design at the group level and heighten the risk associated with heteroscedasticity in a G-RCT. Based on our previous research, we estimate that no more than 20% of members measured at pretest will be missing at posttest, although we will make every effort to obtain posttest data on all individuals, including those who stop attending the sessions. Multiple imputation is now widely regarded as an effective method for replacing missing data, and we will use this approach, adapted for use with a G-RCT. We will employ SAS PROC MI and SAS PROC MIANALYZE to implement these multiple imputation procedures. Advantages of this analysis are that it carries the nominal Type I error rate across a variety of conditions found in G-RCTs, it provides results that correspond to the standard ANCOVA,

except that the standard errors and *df* for fixed effects are constructed to reflect the extra variation and limited *df* due to the G-RCT design; it often has good power compared to the alternatives; and the analysis is simple to conduct and explain. The only disadvantage is that it provides results in the form of adjusted condition means rather than change scores; we do not consider this an important disadvantage.

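### Table 5 calls the T3 assessor blinded, but the same row has that assessor work with peer mentors, who exist only in MBA schools, and no safeguard is described

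*Combined protocol and SAP*

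**What the plan says.** Table 5 (Data Procedures and Process) gives the T3 row a single staff entry: "RA (blinded to group". The row lists three tasks: the self-report survey, one week of accelerometry, and the Health Behaviors Questionnaire. The survey is provided by subjects. The providers of the other two are printed as "Teachers, Peer Mentors, Subjects) (Peer Mentors, Subjects", the first group for the accelerometer and the second for the questionnaire. The T1, T2 and T3 Follow-Up rows are assigned to Team, with no mention of blinding, so T3 is the only masking that the table claims.

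Other sections fix who the mentors are and who collects their data:

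- Sample: "190 older teens will be recruited to serve as peer mentors (19 per school x 10 schools) in the MBA condition".
- Participant Recruitment and Retention: "All teen mentors will attend the same school and reside in the same local community as study participants". For the other arm: "School health teachers at participating schools will provide the comparison delivery method".
- B. Detailed Study Procedures: "Data from peer mentors will be collected by an RA at completion of mentor training", and again at T2 and T3.
- C. Internal Validity: "schools will be randomized for study condition (PBA or MBA".

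**The concern.** Mentors are a feature of one arm only, and the school is the unit of randomization. Meeting mentors at a school, or being due to collect mentor data and finding none, tells the assessor which arm the school is in. The row thus claims blinding and also assigns tasks that disclose the arm.

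Students cannot be masked to whether a peer or a teacher delivered the program, so masking the assessor is the main protection available for measures that staff administer. Section B has survey items read out to students, with staff on hand for queries, which leaves room for influence. The questionnaires scheduled at six months in Table 1 include self-efficacy and self-regulation, the proposed mediators in Aim 5. If T3 were later reported as assessor-blinded, the plan as written would not support the statement.

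**Working it through.** **Step 1. Are mentors in one arm or both?** Inputs from the Sample section: 19 mentors per school, and "10 schools per condition, and 75 students per school".

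- Mentors in MBA schools only: 19 x 10 = 190. Subjects: 2 x 10 x 75 = 1,500. Total: 1,500 + 190 = 1,690. Both the 190 and the 1,690 match the plan.
- Mentors in all 20 schools: 19 x 20 = 380. Total: 1,500 + 380 = 1,880. Neither matches.

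The plan's own counts therefore place mentors in the MBA arm alone.

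**Step 2. What does the T3 row ask of the RA?** Taking tasks and providers in printed order:

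| T3 task | Provided by | Shows the arm? |
|---|---|---|
| Self-report survey | Subjects | No |
| Accelerometer, one week | Teachers, mentors, subjects | Yes, through mentors |
| Health Behaviors Questionnaire | Mentors, subjects | Yes, through mentors |

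The separate T3 Follow-Up row gives the collection of accelerometer data to Team. The RA's accelerometer task is therefore best read as issuing the devices. Two of the three tasks still involve mentors.

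**Step 3. What can the RA infer?** Under the rule that mentors present means MBA and mentors absent means PBA, the planned design classifies 10 of 10 MBA schools and 10 of 10 PBA schools correctly, 20 of 20 in all. Schools are the randomized unit, so a school's arm is the arm of every student in it. The rule needs only one mentor still present at each MBA school, not the full 19.

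**Step 4. Is there a safeguard elsewhere?** Section B says that an RA collects mentor data at all three time-points. It does not say that this is a different person from the RA who sees subjects. No section sets a separate visit, a separate assessor or an order of collection that would keep the T3 RA unaware of the arm.

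**Step 5. Which outcomes are exposed?** The T3 row lists questionnaires and accelerometry. It does not list height, weight or impedance. Table 1 schedules BMI and body fat at six months, and Section B places anthropometry at every time-point, but neither says who takes them at T3.

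**The case against.** The strongest reply is that RA is a role label, not one person. Table 5 refers to training of RAs in the plural, and one RA could see subjects while another sees mentors. The table has also lost its layout in the text available, so whether the entry spanned all three task lines cannot be confirmed. This stands in part. A reader might infer that the blind cannot hold in any school whatever is done, and the documents do not support that, because a second RA would preserve it for subject data. They do not plan one, however, and the row as printed makes no distinction.

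Three further inferences are tempting and should not be drawn:

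- **That PBA schools are revealed when the RA retrieves a teacher's monitor.** The T3 Follow-Up row gives that task to Team. The inference for PBA schools rests on the absence of mentors.
- **That the RA meets 19 mentors per MBA school at T3.** Section B places mentor T3 at the start of the next academic year. Mentors who were in 12th grade may have graduated by then, and no T3 count is given. The remaining mentors would still disclose the arm.
- **That the primary BMI outcome is assessed unmasked at T3.** The row lists no anthropometry. The Data Analysis section also places the BMI comparison at T2, whereas the Sample section places it at six months.

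It is also fair to say that accelerometer counts are recorded by a device, that staff are trained before each time-point, and that the pre-intervention survey uses scripted directions and student-completed paper forms. These limit the scope for influence but do not make the assessor blinded.

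**Conclusion.** The T3 row is wrong as written. Its list of tasks removes the blinding that it claims, and this is the only assessor masking stated in Table 5. If the row is followed as printed, mentor presence or absence identifies the arm in all 20 planned schools.

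This rests on three assumptions: that the single staff entry covers the whole row, that the RA knows mentors belong to MBA, and that at least one mentor remains at each MBA school at T3. The first is the weakest, but if different RAs are intended the plan should say so, and the same edit resolves it.

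The consequence is limited. Exposure is mainly to questionnaires that staff administer and less to accelerometry. It extends to BMI or body fat only if the same RA takes those measures at T3. The documents give no basis for the size or direction of any resulting bias, and none is claimed here.

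**What to change.** Split the T3 row of Table 5. The blinded RA handles only the subject (mentee) lines. The mentor and teacher lines go to Team, which already covers T1, T2 and T3 Follow-Up, and are kept apart from subject collection. Put the blinding statement on the subject line only. Make the Section B sentence on mentor data agree, and state that the blinded RA has not collected mentor data at the same school at T1 or T2. If height, weight and impedance are taken at T3, add them to the row and name who takes them. Recording the RA's guess of arm is optional.

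If the split is not wanted, delete the blinding claim and report T3 assessors as unmasked.

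The cost is mostly scheduling, with no change to sample size, measures or analysis. Some extra visits are possible, because monitors are worn for 7 days and each participant needs two school visits. Subject monitoring already rotates over three weeks per school. A wholly separate round for mentors and teachers after the subjects would add about a week and up to 2 x 20 = 40 visits. Having Team work alongside the existing weeks, but apart from subject collection, should need fewer. Students may still disclose their arm in conversation, so the split removes the built-in disclosure but does not guarantee the blind.

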### C. Internal Validity

To avoid study bias, schools will be randomized for study condition (PBA or MBA). The primary analysis will follow intention-to-treat principles. Randomization carries the expectation that the study conditions will be equivalent at pretest with respect to known and unknown prognostic factors. As a result, removing randomized groups or members from the analysis runs the risk of tampering with this balance and introducing bias. Further, loss of one or more groups could create an unbalanced design at the group level and heighten the risk associated with heteroscedasticity in a G-RCT. Based on our previous research, we estimate that no more than 20% of members measured at pretest will be missing at posttest, although we will make every effort to obtain posttest data on all individuals, including those who stop attending the sessions. Multiple imputation is now widely regarded as an effective method for replacing missing data, and we will use this approach, adapted for use with a G-RCT. We will employ SAS PROC MI and SAS PROC MIANALYZE to implement these multiple imputation procedures. Advantages of this analysis are that it carries the nominal Type I error rate across a variety of conditions found in G-RCTs, it provides results that correspond to the standard ANCOVA,

except that the standard errors and *df* for fixed effects are constructed to reflect the extra variation and limited *df* due to the G-RCT design; it often has good power compared to the alternatives; and the analysis is simple to conduct and explain. The only disadvantage is that it provides results in the form of adjusted condition means rather than change scores; we do not consider this an important disadvantage.

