#### **IV. Measurement/Instrumentation**

**Measures.** Our measures are comprised of items adapted from published studies and preliminary studies. All measures have been used with adolescents residing in rural or Appalachian settings and show acceptable psychometrics: internal consistency reliability  $\alpha$  of .75-.94; face validity, predictive validity, and content validity, and/or construct validity are established (See Table 1).

Table 1. Variables, Instruments, Reliability, Validity and Data Collection Times for the Teens

Variable from Theoretical Framework	Instrument/ Source of Data	Cronbach's Alpha	Type of Validity	Data Collection Times			Measure Used in Statistical Analysis
				Pre	3 mo	6 mo	
Demographics (potential covariates/moderators)	Demographic questionnaire	NA	NA	X			Item ratings/answers
Behavioral Outcomes	Healthy Lifestyle Behaviors Scale	.84 and ↑	Face, Content Construct	X	X	X	Total score on the Healthy Lifestyle Behaviors Scale
	Accelerometer Activity			X	X	X	7 days of daily activity
Behavioral Outcomes	Daily Lifestyle Patterns		Content, Construct	X	X	X	4-item questionnaire
Primary Health Outcomes	Body Mass Index, BMI%, Body Fat%	NA	NA	X	X	X	BMI, BMI%, Bio Electronic Impedance
Psychological Determinants	Physical Activity Outcome Expectations	.86-.97	Construct Predictive	X	X	X	Total Score on each of 8 sub-scales: relaxation, fitness, competition, social growth, social continuation, health Total Score
	Self-Efficacy for Physical Activity	85-.94	Predictive	X	X	X	
Self-Regulation	Self-Regulation for Physical Activity	.89-.95	Content and Construct	X	X	X	Total score on each 6 subscales: goal setting, self-monitoring, overcoming barriers, time management, self-reward, planned support
	Social Support	.75-.88	Face and Construct	X	X	X	Total Score
Environmental Determinants	Perceived Environment for Physical Activity	Test-retest (59%-74%)	Construct	X	X	X	Total score on each of 1 subscale: neighborhood

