## D. Data Analysis

We will use Linear Mixed Models (LMMs) and Generalized Linear Mixed Models (GLMMs) to account for various levels of correlation among participants. Power for this study was based on power for the primary analysis comparing BMI outcomes at T2 between the two groups, adjusting for baseline BMI values. Such an approach is also known as a “mixed-model ANCOVA.” We will implement these models using SAS PROC MIXED and GLIMMIX, Version 9.3.

Research questions guiding the analysis of cognitive interview data for this aim are: Were there specific components of the intervention that appealed more than others? Were there any specific components which were not liked or were objectionable in anyway? Was there an age- or gender-related difference in reactions to components of the intervention?

To analyze mediating effects of self-regulation and self-efficacy on health outcomes and M/V physical activity, we will use bootstrapping techniques to determine significant relationships between the potential mediating variables and outcomes of interest.

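### Does leaving the school term and the pooling degrees of freedom out of the imputation description put the Type I error of the primary BMI test at risk?

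*Combined protocol and SAP*

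**What the plan says.** Section C expects that "no more than 20% of members measured at pretest will be missing at posttest". For the missing values it chooses multiple imputation and says "we will use this approach, adapted for use with a G-RCT", citing reference 81, a paper on how clusters are modelled in multiple imputation for cluster randomized trials. The tools are named: "We will employ SAS PROC MI and SAS PROC MIANALYZE to implement these multiple imputation procedures".

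The section then lists the merits of the analysis. One is that "it carries the nominal Type I error rate across a variety of conditions found in G-RCTs". Another is that standard errors and df for fixed effects allow for the extra variation and limited df of the group-randomized design.

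Section D (Data Analysis) describes the outcome model, a mixed-model ANCOVA adjusting for baseline BMI: "We will implement these models using SAS PROC MIXED and GLIMMIX, Version 9.3". The Sample section gives the design inputs: "we estimate that the school-level ICC for BMI among 9th graders in Appalachian Ohio counties is 0.023", and "With these assumptions, 10 schools per condition, and 75 students per school, we will have 82% power to detect a modest intervention effect".

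**The concern.** Four things are not written down: how school enters the imputation model, which other variables enter it, the number of imputations, and the complete-data df used in pooling.

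With 20 schools the between-school df are only 20 − 2 = 18, so two mistakes would be possible in principle. An imputation that ignores school draws imputed values with too little between-school variance, and the standard error is then too small. Separately, pooling with large-sample df compares a statistic that has about 18 df with a normal critical value. Either would fall on the primary BMI test.

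The advantages listed in Section C read most naturally as properties of the mixed-model ANCOVA. They reach the pooled test only if the imputation and pooling steps preserve them, so the plan could seem to claim a property it has not secured.

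**Working it through.** **Inputs from the documents.** 10 schools per condition and 75 students per school; ICC for BMI 0.023; over-time correlation 0.70; 30% of variance explained by age and gender; effect 0.2 SD; stated power 82% (all Sample). Up to 20% missing (Section C).

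**Assumed.** Two-sided 5% alpha. Residual ICC of 0.023 after baseline adjustment, which holds if school means also correlate 0.70 over time; the range 0.005 to 0.045 was examined.

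**The plan's own power figure.** With m students per school, g = 10 schools per condition and residual variance f,

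Var = 2f[(1 − ICC) + m·ICC]/(m·g).

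Taking f = 2(1 − 0.70) = 0.60 and m = 75: Var = 1.2 × (0.977 + 1.725)/750 = 0.00432, SE = 0.0658, and the noncentrality is 0.2/0.0658 = 3.04. On 18 df this gives 82.0% power, which matches. With f = 1 − 0.70² = 0.51, power is 87.7% at 75 per school and 84.8% at 60.

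**The df question alone.** P(|t₁₈| > 1.96) = 6.6%. In simulation with no missing data, the ANCOVA had a Type I error of 4.7% on 18 df and 6.1% against 1.96. The 6% figure therefore comes from the choice of df, whether or not anything is imputed.

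**Type I error of the pooled test.** Null simulations: 20 schools of 75, ICC 0.023, 20% missing completely at random, REML mixed-model ANCOVA, Rubin's rules. The first figure in each cell uses 20 imputations and the second, from a separate simulation, uses 5. Each rests on 12,000 runs (Monte Carlo SE about 0.15 to 0.26 points).

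| Imputation model | 18 df | small-sample pooled df | large-sample pooled df |
|---|---|---|---|
| random school, condition, baseline BMI | 4.8 / 4.7% | 4.4 / 4.3% | 6.3 / 6.1% |
| fixed school, baseline BMI | 3.0 / 3.2% | 2.8 / 2.9% | 4.2 / 4.2% |
| school left out, condition kept | 7.0 / 7.1% | 6.4 / 6.4% | 9.2 / 8.9% |
| school and condition both left out (5 imputations only) | 2.7% | 2.4% | 3.7% |

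Making missingness depend on baseline BMI moved these by no more than about 0.5 point. The number of imputations made almost no difference.

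**Sensitivity with school included and 18 df.**
- Fixed school: 3.8%, 2.6% and 2.1% at residual ICC 0.045, 0.012 and 0.005.
- School effects uncorrelated over time (4,000 runs): 5.6% with random school and 4.4% with fixed school, against 5.5% with complete data in the same runs.

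**Power at 0.2 SD, 18 df, ICC 0.023.**

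| Residual variance | observed-data ANCOVA | random school | fixed school |
|---|---|---|---|
| 0.357 (0.51 × 0.70) | 94.5% | 94.3% | 92.5% |
| 0.51 | 84.9% | 84.6% | 80.8% |
| 0.60 | 78.8% | 78.4% | 73.7% |

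Fixed effects widen the standard error by about 9%. At residual variance 0.51 the loss is 84.9 − 80.8 = 4.1 points; at residual ICC 0.045, 0.012 and 0.005 it is 4.3 (67.3 to 63.0), 3.2 (93.8 to 90.6) and 2.0 (97.9 to 95.9) points.

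**Which rows follow the plan.** The plan says the imputation is adapted to the group-randomized design, which rules out the two rows without school. It also says df reflect the limited number of groups, which points to the first two columns. The cells that remain run from 2.8% to 4.8%.

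**The case for a change.** The strongest case for a change is that this is the primary test in a trial with few clusters, that the details are missing, and that the cited title on fixed-effects modelling of clusters does not tell a programmer which model to run. Even with school included, Type I error spans about 3% to 6% and the fixed-effects choice costs some power. Choices left open could be made after outcomes are seen, and writing them down is cheap.

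Much of this stands as description. The details are not given, and an explicit pooling df would be useful to whoever programs the analysis, particularly as the limited-df statement is made for the analysis model and is not tied to the pooling step.

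It does not show that following the plan produces a wrong test. The upper end of the 3% to 6% span needs large-sample df, against the section's own statement about limited df. The 7% to 9% range needs school omitted, against the stated adaptation, and also needs condition retained; with both omitted the test is conservative. The power loss is a known price of one legitimate choice and brings no false-positive risk when design-based df are used.

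A fuller specification would also run into a separate matter. Three-month BMI looks like a natural auxiliary variable for a 6-month outcome, which is the time point in the Sample section. Section D places the primary comparison at T2, which Table 5 defines as 3 months; on that text, 3-month BMI is the outcome being imputed.

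**Conclusion.** No change follows. The plan commits to an imputation that respects the schools and to df that reflect their number. Analyses that keep to this give a Type I error of about 3% to 5% at a residual ICC of 0.023, so the test is nominal or mildly conservative. Pooling on large-sample df would give about 4% to 6%, at most a little over one point above nominal. Entering school as a fixed effect costs about 2 to 4 points of power at residual variance 0.51, and about 5 points (78.8% to 73.7%) at 0.60, where power is below 80% before any imputation effect.

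These sizes rest on a two-sided 5% alpha, 20% missing at random given the modelled variables, and a residual ICC that the documents do not state. What is missing is implementation detail, and no stated rule or figure on this point is shown to be wrong. The primary time point and the two stated power figures (82% in Sample; 82.5% under Participant Recruitment and Retention) are separate questions, and this conclusion does not depend on them.
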